7. STUDY TREATMENT

7.1 Treatment Schedule/Administration

Cytarabine administration will be recorded including, but not limited to, date of administration, dose (total and mg/m²) and any changes in dose administration (e.g., interruption or reduction in dose due to an adverse event). Cytarabine will be scheduled to be given IV q12h on the first three days of each 28-day treatment cycle, unless there has been a scheduled modification of administration due to not meeting treatment parameters, such as hematologic recovery or toxicity. The product will be administered per institutional standard in terms of nursing administration and pharmacy preparation. Antiemetic medication(s) should be given 30-60 minutes prior to administration of cytarabine per institutional guidelines, and agents may be modified for individual patients based on risk factors and previous antiemetic responses. Eye drops (steroid or artificial tears) should be given prior to cytarabine and continued for 48 hours after last dose of cytarabine given. Prophylactic antimicrobials should be given as standard of care. Pegfilgrastim 6 mg SQ (or equivalent) should be given once 48 hours +/- 24 hours after completion of chemotherapy. Filgrastim (or equivalent) may be given as an alternative (5 mcg/kg rounded to vial size daily until WBC recovery). If patient is unable to receive these aforementioned medications, the reason should be documented.

Patients will be monitored for cerebellar toxicity using NCI CTCAE v5 toxicity grades while admitted for high dose cytarabine. Patients will be asked to sign his/her name prior to each dose of chemotherapy. If there is suspicion of neurotoxicity, a provider should assess the patient as clinically indicated.

7.2 Dose Calculations

Chemotherapy will be dosed according to institutional standard, unless otherwise specified. Generally, cytarabine will be dosed on actual/total body weight, and body surface area (BSA) will be capped at 2.4 m².

BSA will be documented per Mosteller formula.

$$\text{BSA (m}^2\text{)} = \sqrt{\text{height (cm)} \times \text{weight (kg)}}/3600$$

7.3 Supportive Care

7.3.1 Supportive Care Guidelines

Subjects should receive full supportive care, including transfusions of blood products, antimicrobials, antiemetics, antidiarrheals, eye drops, analgesics, etc., when appropriate. Supportive care will be administered to all study subjects per institutional guidelines. Subjects will be counseled on the expected side effects of cytarabine and what to do if/when these occur.

Growth factors (granulocyte-colony stimulating factor [G-CSF]) should be given if able, according to the institutional standard of care.¹⁷ Pegfilgrastim (or biosimilar product) 6 mg SQ once 48 hours +/- 24 hours (or on-body injector on the last day of chemotherapy) is generally used for primary prophylaxis of febrile neutropenia. If patient is unable to obtain pegfilgrastim, then filgrastim (or biosimilar) 5 mcg/kg rounded to vial size shall be administered SQ daily until ANC recovery.

Antiviral, antifungal, and antibacterial prophylaxis and treatment should follow conventional guidelines and institutional guidelines.¹⁸ In general, levofloxacin, fluconazole (or mold-active azole if patient has history of IFI), and valacyclovir (or acyclovir) are started when ANC is approximately 500/mm³ or below and continued until count recovery. See Appendix B for UF Health Shands Hospital transfusion guidelines.

7.3.2 Concomitant Therapy

Relevant medical history should be obtained at screening and include prior AML treatment history. Medications will be reviewed at screening for FLT3 and IDH 1/2 inhibitors to assess exclusion criteria.

The use of concomitant therapy will be collected, such as supportive care (e.g., growth factors, antimicrobials, eye drops) throughout consolidation therapy and will be administered per institutional guidelines or patient-specific treatments per the treating physician.

7.3.3 Infections

Chemotherapy puts the patient at higher risk for bacterial, viral, or fungal infections, which are potentially life-threatening. Prophylactic antimicrobial medications and prophylactic granulocyte colony stimulating factor will be initiated per institutional guidelines if able, and patients will be closely monitored for signs of infections and will receive early and appropriate treatment per standard of care. Infections will be scored according to infections listed in Appendix A.

7.3.4 Prohibited Concomitant Therapy

Supportive care measures consistent with optimal subject care will be permitted throughout the study, as long as the therapy is not included in this section as prohibited.

Subjects are prohibited from receiving the following therapies during the Screening and Treatment Phase of this trial:

- FLT3 inhibitors, e.g., midostaurin, sorafenib, gilteritinib, or any investigational FLT3 inhibitor)
- IDH 1 and IDH2 inhibitors, e.g., ivosidenib, enasidenib or any investigational IDH inhibitor

7.3.5 Hematopoietic Stem Cell Transplantation Treatment

Subjects may undergo allogeneic stem cell transplant after study entry; at the start time of conditioning therapy, the subject will be removed from the study. The time to next treatment (date of conditioning) will be recorded. The conditioning regimen, donor type and graft source during the allogeneic HCT period will be recorded.

7.4 Dose Modifications

The National Cancer Institute (NCI) Common Toxicity Criteria (**v5.0**) for Adverse Events (CTCAE) will be used to grade toxicity (<http://evs.nci.nih.gov/ftp1/CTCAE/About.html>).³

Subjects will generally receive cytarabine 1000 mg/m² IV q12h x 6 doses. Dose modifications may occur per physician discretion. If dose or duration is different than stated above, the reason should be recorded.

7.4.1 Non- Hematologic Toxicity

Dose modifications or interruptions may occur per standard of care or per the treating physician based on patient tolerability.

7.4.2 Hematologic Toxicity

Dose modifications or interruptions may occur per standard of care or per the treating physician based on patient tolerability.

8. TREATMENT DISCONTINUATION

8.1 Screen Failures

Subjects who sign informed consent, but do not meet eligibility criteria, or withdraw prior to eligibility being verified, and undergo at least some of the screening procedures will be considered screening failures. Subjects who sign informed consent and are verified as eligible, but do not proceed to formal registration will be considered “unregistered.” A record of screen failures and unregistered subjects will be maintained by the study site.

8.2 Criteria for Study Treatment Discontinuation

Subjects who discontinue participation in the clinical study on their own or subjects who are withdrawn by the investigator, for reasons other than completion of treatment, proceeding to HCT, relapse or toxicity, will be defined as premature withdrawals. The end of treatment data will be collected if available at last visit if confirmed relapse, death, or proceeding to HCT. For those with toxicity that end before planned last cycle, data will be collected up to the end of treatment date and AE data will be collected until 28 days following the most recent dose of study treatment or initiation of a new chemotherapy regimen (whichever comes first).

Subjects will be followed for long term data every 3 months (\pm 28 days) until relapse, death or until 48 months after induction therapy (whichever comes first).

A subject will be discontinued from protocol therapy under the following circumstances:

- Any adverse event which, in the Investigator's opinion, requires termination of the chemotherapy
- Disease relapse
- If subject proceeds to allogeneic HCT
- The subject uses illicit drugs or other substances, or takes part in activities that may, in the opinion of the Investigator, have a reasonable chance of contributing to toxicity or otherwise interfering with results
- The subject is lost to follow-up
- Death
- Development of an intercurrent illness or situation which would, in the judgment of the investigator, affect assessments of clinical status and study endpoints to a significant degree

The Investigator will make every reasonable effort to keep each subject in the study unless it is in the subject's best interests to discontinue participation. If a subject is removed from the study or declines further participation, all EOT evaluations should be performed if the subject is willing and able to be assessed. A description of the reason(s) for withdrawal from the study must be recorded on the case report form (CRF). The Investigator should also ensure that all subjects are followed up for survival status after the Final Visit.

Subjects who discontinue following entry will have relevant information completed and recorded on the CRF. All subjects who discontinue because of adverse events or clinically significant laboratory abnormalities should be followed up until they recover or stabilize, and the subsequent outcome will be recorded. If any subject should experience an unexpected serious adverse event during the trial or within 28 days of stopping study treatment, the Investigator will inform the UF Health Data Integrity and Safety Committee.

8.3 Replacement of Subjects

Subjects will be replaced if they have not received any doses of study drug prior to their withdrawal.

9. BIOLOGICAL SPECIMENS AND CORRELATIVES

9.1 Source of Specimens

Peripheral blood (<5 mL) will be collected in subjects on the prospective arm for exploratory analysis. Only one sample is needed, and this will be during the pre-admission labs prior to first consolidation chemotherapy cycle.

All correlative studies will be performed in [name] laboratory at University of Florida. Peripheral blood samples will be collected and analyzed in [name] laboratory. We will use genotype patient samples for the 4 SNPs that are part of ACSS score and compute ACSS score for each patient and patients will be classified into having a low (<0) or high ACSS (≥ 0).

9.2 Correlative Studies

We will compare the ACSS score for association with clinical endpoints using appropriate statistical tests as used in our previous work. Statistical analysis will be performed to compare overall-survival (OS), between ACSS groups using Cox regression and Fisher's exact test for toxicity endpoints and Wilcoxon test for association of ACSS score with duration or neutropenia/thrombocytopenia.

9.3 Preparation, Shipment and Storage of Specimens

Three to five mL of peripheral blood will be collected in EDTA tube on pre-admission or admission day of C1D1 of HiDAC consolidation. Storage in -80 deg C is preferred but sample can be kept at 40 deg C to send to the laboratory. Specimens will be processed after funding is obtained.

10. STUDY DRUG INFORMATION¹⁴

10.1 Study Drug Name

Cytarabine (Cytosar®); multiple manufacturers; aka cytosine arabinoside, Ara-C.

10.2 Identification

Cytarabine, initially developed by Pfizer, is a standard of care chemotherapy used for intravenous administration in the management of AML patients. Cytarabine is a colorless solution that is diluted in 0.9% sodium chloride. At high doses, it is usually diluted in 250 mL IV and given over 2-3 hours. Preparation and administration is per institutional guidelines and policies as applicable.

10.3 Packaging and Labeling

Vials are supplied from institution's wholesaler via commercial supply. Preparation and labeling of IV infusion will follow institutional policies and procedures.

10.4 Drug Supply

Vials are supplied from institution's wholesaler via commercial supply.

10.5 Storage, Handling and Dispensing

Storage, handling and dispensing of cytarabine and other supportive care medications will follow institution's policies and procedures. This product will be given per SOC except for the interval/days for the HiDAC 123 arm. The pharmacist will verify and dispense the medication(s) and nursing will administer medications as above per institutional policies and procedures.

10.6 Drug Ordering and Accountability

Drug product ordering and accountability will follow institutional policies and procedures.

10.7 Infusion Reactions

Severe allergic reactions are very rare with cytarabine (<1%). Nurses should monitor the patient for any signs/symptoms of anaphylaxis and notify provider if these occur. Patient should be treated per conventional and institutional guidelines for treatment of anaphylaxis. Two adverse effects that patients should be monitored for while receiving cytarabine and shortly after are ocular and neurotoxicity as stated previously in protocol.

10.8 Contraindications

Allergy to cytarabine, patients unable to monitor for ocular or neurotoxicity or any other condition that the treating physician feels is a contraindication to receiving high doses of cytarabine.

10.9 Special Warnings and Precautions for Use

Bone marrow suppression and associated complications (e.g., bleeding and infection), chemical conjunctivitis, and cerebellar toxicity are the most significant complications of high-dose cytarabine. Cytarabine is a chemotherapy agent, so standard universal precautions should be followed in terms of handling and administering the product and handling any bodily secretions and blood of patients receiving cytarabine per SOC and institutional policies and procedures.

There are no clinically significant drug interactions with single agent cytarabine regimens.

10.10 Adverse Event Profile

Most Frequent Adverse Reactions

Anorexia	fever	thrombocytopenia
Nausea	rash	anemia
Vomiting	thrombophlebitis	neutropenia
Diarrhea	oral mucositis	infections

Less Frequent Adverse Reactions

Sepsis	esophageal ulceration	shortness of breath
Bleeding	esophagitis	alopecia
conjunctivitis	chest pain	anaphylaxis
urinary retention	pericarditis	allergic edema
renal dysfunction	bowel necrosis	pruritis

Neuritis	abdominal pain	urticaria
neurotoxicity	pancreatitis	hand-foot syndrome
Headache	hepatic dysfunction	skin ulceration
Dizziness	jaundice	

11. ADVERSE EVENTS

11.1 Definitions

11.1.1 Adverse Event

The term “adverse event” (AE) includes any sign, symptom, syndrome, or illness that appears or worsens in a subject during the period of observation in the clinical study and that may impair the wellbeing of the subject. The term also covers laboratory findings or results of other diagnostic procedures that are considered to be clinically significant (e.g., that requires unscheduled diagnostic procedures or treatment measures, or result in withdrawal from the study). An AE is therefore any unfavorable and unintended symptom or disease temporally associated with the administration of an investigational product, whether or not related to that investigational product.

The adverse event may be:

- A new illness/condition;
- Worsening of a sign or symptom of the condition under treatment, or of a concomitant illness/condition;
- An effect of the study drug; or
- A combination of 2 or more of these factors.

No causal relationship with the study drug or with the clinical study itself is implied by the use of the term “adverse event.”

The Investigator or his/her designee will assess for occurrence of AEs during hospitalization and each outpatient visit (or via telephone survey if patient is unable to return to clinic at the planned time). AEs related to cytarabine will be recorded in the subject CRF. AEs will be described by duration (start and stop dates and times), severity, outcome, treatment and relation to study drug, or if unrelated, the cause.

Surgical procedures themselves are not adverse events; they are therapeutic measures for conditions that require surgery. The condition(s) for which the surgery is required may be an adverse event. Planned surgical measures permitted by the clinical study protocol and the condition(s) leading to these measures are not adverse events.

When a clear diagnosis is available that explains the abnormal objective findings, this diagnosis will be recorded as an adverse event and not the abnormal objective findings (e.g., viral hepatitis will be recorded as the adverse event and not the transaminase elevation). If a definitive diagnosis is not available, then the sign(s) (e.g., clinically significant elevation of transaminase levels) or symptom(s) (e.g., abdominal pain) will be recorded as the adverse event.

Adverse events fall into the categories “serious” and “non-serious.”

11.1.2 Serious Adverse Event

A serious adverse event is one that at any time during the period of observation:

- Results in death
- Is life-threatening (defined as an event in which the subject was at risk of death at the time of the event; it does not refer to an event which hypothetically might have caused death if it were more severe)
- Requires inpatient hospitalization or causes prolongation of existing hospitalization
- Results in persistent or significant disability/incapacity
- Is an important medical event, defined as a medical event that may not be immediately life-threatening or result in death or hospitalization but, based on appropriate medical and scientific judgment, may jeopardize the subject or may require intervention (e.g., medical, surgical) to prevent one of the other serious outcomes listed above. Examples of such events include but are not limited to intensive treatment in an emergency department or at home for allergic bronchospasm; blood dyscrasias or convulsions that do not result in hospitalization. “Medically important” should be marked only if no other serious criteria are met.

An “unexpected SAE” is any SAE for which the nature, specificity or severity is not consistent with the currently known adverse event profile of cytarabine.

Clarification of the difference in meaning between “severe” and “serious”

The term “severe” is often used to describe the intensity (severity) of a specific event (as in mild, moderate, or severe myocardial infarction); the event itself, however, may be of relatively minor medical significance (such as severe headache). Any grade ≥ 3 adverse event per CTCAE is generally considered severe AE. This is not the same as “serious,” which is based on the outcome or action criteria usually associated with events that pose a threat to life or functioning. Seriousness (not severity) serves as a guide for defining regulatory reporting obligations.

11.1.3 Non-Serious Adverse Event

A non-serious adverse event is any adverse event not meeting any of the serious adverse event criteria.

11.2 Period of Observation

Following the subject's written consent to participate in the study, all SAEs must be collected, including those thought to be associated with protocol-specified procedures. Collection of all SAEs must continue for at least 28 days after the last dose of study treatment or until initiation of new chemotherapy regimen (whichever comes first).

The investigator will begin collecting ocular or neurologic toxicities of any grade related to cytarabine and other grade 3-5 non-hematologic and hematologic toxicities and associated toxicities, such as bleeding and infection once administration of cytarabine is initiated. Treated subjects, including those who were prematurely discontinued from the study, will be monitored for any adverse events that occur during the study until 28 days following the most recent dose of study treatment or initiation of a new chemotherapy treatment (whichever occurs first). If another course of anti-cancer therapy is initiated prior to the 28 day follow-up period visit, collection of adverse events will no longer be performed, with the exception of events that may be possibly, probably, or definitely related to cytarabine or are clinically significant. If AE is deemed related to the study intervention and ongoing at the end of the monitoring period, the event will be monitored until resolution, returns to baseline or in the investigator's opinion, deems the event is unlikely to resolve due to the patients underlying disease.

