In 2006, the American Society of Clinical Oncology published guidelines that recommended prophylactic white blood cell growth factors after AML consolidation chemotherapy regimens. Bradley, et al published results of patients who did or did not receive prophylactic growth factor after first cycle of consolidation chemotherapy with at least 1000 mg/m² cytarabine q12h D1, 3, 5.¹⁵ Patients who received granulocyte colony stimulating factor (GCSF) had less readmissions for febrile neutropenia vs patients who did not receive GCSF (14% vs 37%).

In general, the neutrophil nadir starts around Days 7-10 after HiDAC consolidation, and most patients start to recover neutrophils between Day 21 and 24, but hematologic recovery

depends on various factors, such as age, amount of prior treatments, prior antecedent hematologic disorder, etc. The use of GCSF has decreased the time to hematologic recovery. Sierra, et al showed median time to neutrophil recovery after HiDAC consolidation therapy to be 17 days if given GCSF.¹⁶ In Jaramillo, et al, the median time to neutrophil recovery after 1-3 HiDAC consolidation(s) was 21-22 days in HiDAC 135 cohort compared to 17-18 days for subjects in the HiDAC 123 arm. Dumas, et al reported a median time of neutrophil recovery of 14-16 days with HiDAC 123 compared to 17-19 days with HiDAC 135.²

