3. STUDY DESIGN

3.1 Study Overview

This is a single center, open-label, non-randomized phase II study. Twenty nine (29) subjects are planned to be enrolled in this study. Each subject will be administered cytarabine 1000 mg/m² IV q12h x 6 doses on Days 1-3 in the hospital during the consolidation treatment phase. Subject may receive up to four consolidation cycles. Subjects will have laboratory and toxicity assessments as clinically indicated (at baseline, then daily while inpatient and ideally every 48 hours after hospital discharge +/- 24 hours until count recovery from each cycle). These subjects will be compared to 29 historical controls [matched by age (within 3 years), gender (male or female), PS (Karnofsky: 90-100, 70-80, or 50-60) and number of HiDAC cycles received] who received HiDAC 135 from the time period of 2/1/2017-2/1/2019.

Screening data will be reviewed to determine subject eligibility. Subjects who meet all inclusion criteria and none of the exclusion criteria and who have consented will be entered into the study. The following treatment regimen will be used for prospective arm: cytarabine 1000mg/m² IV q12h x 6 doses (Days 1-3) for up to four cycles.

Historical arm subjects will have received cytarabine 1000 mg/m² IV q12h x 6 doses (Days 1, 3, and 5) for up to four cycles from the time period of 2/1/2017-2/1/2019.

Total duration of subject participation will be up to six months from start of first consolidation cycle (each cycle is 28 days, but more time may be required allowing extra time for delayed count recovery in some patients); study participation will end when subject recovers neutrophils and platelets after last administered cycle of chemotherapy, is admitted for conditioning chemotherapy for HCT, dies, or withdraws consent (whichever comes first). However, subjects will be followed every 3 months (\pm 28 days) for up to 48 months after start of induction to determine long-term outcomes. Total duration of the study is expected to be 60 months.

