6) Document supportive care medications (pegfilgrastim or equivalent 48 hours +/- 24 hours after chemo ends; antimicrobial prophylaxis when neutropenic and other anti-infectives needed, eye drops until 48 hours after cytarabine ends, etc.) Supportive care medications and blood transfusions should be documented throughout and for 28 days after last treatment.							
7) Monitoring for SAEs at the time of consent and AEs collection will start the day patient starts cycle 1 of consolidation chemotherapy and continuing throughout the study. Subjects who have received at least one dose of study drug and discontinue prematurely (regardless of reason) will be monitored for any adverse events that occur during study until 28 days following the most recent dose of study treatment or initiation of a new chemotherapy regimen (whichever comes first). If a SAE or AE that is deemed related to the study intervention and ongoing at the end of the monitoring period the event will be monitored until resolution, event returns to baseline or in the investigator's opinion, deems the event is unlikely to resolve due to the patients underlying disease.							
8) End of treatment visit will occur in subjects who complete 3-4 cycles of consolidation or at study withdrawal (for example, at HCT conditioning, relapsed disease or if ended earlier than planned due to toxicity or physician discretion). Other assessments will be performed as necessary by the treating physician. Outside lab results may be collected if subject unavailable to travel to the institution.							
9) All subjects will be followed for long term outcomes until: relapse, death, or until closure of study.							
10) This data may be collected via telephone interview.							
Abbreviations: SOC= standard of care; PRN = as needed; BSA = OS = overall survival; SAE = severe adverse effects, AEs = adverse effects; HCT = hematopoietic stem cell transplant							

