6.3 Follow up Evaluations

Subjects will have follow-up visits for the evaluation of adverse events, labs, etc. per standard of care (after discharge from chemotherapy administration, generally every 48 hours +/- 24 hours until neutrophil and platelet recovery after each consolidation chemotherapy cycle). Patients will be evaluated prior to starting next chemotherapy cycle, then admitted for chemotherapy and monitored while inpatient.

If the subject is unavailable to travel to the institution (if situation changes from study inclusion criteria after subject starts first consolidation cycle), the visit may be made via telephone interview to review for adverse event resolution or the occurrence of any new adverse events, and outside labs reviewed if collected. Additionally, medical records may be requested with permission of the subject to complete remote visit reporting e.g., if admitted to an outside institution due to complications of chemotherapy.

If the subject is at the treating facility and the physician decides to hold, reduce, or omit the dose completely, the following procedures should be performed:

- Document reason for delay, decreased or missed doses
- AE assessment
- Hematology laboratory evaluations: complete blood count (CBC) including hemoglobin, hematocrit, white blood cell (WBC) with differential and platelet count

If study therapy is discontinued before planned, disease assessments will be performed as clinically indicated, such as suspicion of relapse. Reason for discontinuation should be documented, e.g., relapse, proceeding to HCT, unexpected toxicity/poor tolerance of chemotherapy, etc. Subjects will continue to be followed every 3 months (\pm 28 days) for survival data up to 48 months after induction chemotherapy is started, or until relapse or death (whichever comes first). Following discontinuation of study therapy for any reason, report the date as appropriate (date of confirmed relapse, date of death, date of start of HCT conditioning, or recovery from last planned or unplanned cycle).

If a subject becomes unreachable during the course of the study, the investigator or study team will make a reasonable effort to contact the subject and document each attempt. If these attempts are not successful, the subject may be declared "lost to follow up." For subjects lost to follow-up, the termination date will be the date of last contact with the subject.

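### The 28-day end of AE and transfusion collection conflicts with follow-up to count recovery, so new events in subjects still cytopenic after Day 31 are not clearly required to be captured

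*Combined protocol and SAP*

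**What the plan says.** Two places set a fixed end of collection.

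- Section 11.2, which covers all treated subjects and not only early stoppers, says they "will be monitored for any adverse events that occur during the study until 28 days following the most recent dose of study treatment", or until new chemotherapy if that comes first.
- Section 6.1, footnote 6: "Supportive care medications and blood transfusions should be documented throughout and for 28 days after last treatment".

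Other places tie follow-up to count recovery, or leave the end open.

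- Section 3.1 ends participation at neutrophil and platelet recovery after the last cycle (or at HCT conditioning, death or withdrawal of consent), within six months. It notes that "more time may be required allowing extra time for delayed count recovery in some patients".
- Section 6.3 schedules visits for adverse events and labs, "generally every 48 hours +/- 24 hours until neutrophil and platelet recovery after each consolidation chemotherapy cycle".
- Section 6.1, footnote 7: "AEs collection will start the day patient starts cycle 1 of consolidation chemotherapy and continuing throughout the study". Its own 28-day limit is attached to subjects who discontinue prematurely.
- Section 11.2 on serious events: "Collection of all SAEs must continue for at least 28 days after the last dose of study treatment", unless a new regimen starts first. This is a minimum, not a closing date.

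Section 8.2 adds a third rule: "For those with toxicity that end before planned last cycle, data will be collected up to the end of treatment date", with AE data alone running on to 28 days. Later in the same section, subjects who discontinue because of adverse events are to be followed until they recover or stabilize. Section 6.3 asks for the date of recovery from the last cycle.

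**The concern.** Section 10.9 names bleeding and infection as complications of marrow suppression, so the period at risk lasts as long as the cytopenia. A 28-day clock can stop before that period ends. Take a subject still neutropenic on Day 31 of the last cycle who has a new infection, or needs platelets, on Day 35. Under the AE sentence in 11.2 and the end point in footnote 6, neither event has to be recorded. Under 3.1, 6.3 and footnote 7, the subject is still in the study and still being seen. Staff could reasonably apply different cut-offs to different subjects.

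The endpoints at stake are the secondary safety comparisons in 2.2.2: infections, febrile neutropenia, transfusions per cycle, readmissions, length of stay and grade 3-5 toxicity. The thrombocytopenia endpoint is also touched. The synopsis (Efficacy Assessments) accepts platelet recovery only without a transfusion in the previous 7 days, so a recovery dated after Day 31 needs a transfusion record that runs past Day 31.

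**Working it through.** **Inputs.** Mean duration of neutropenia 16 days (HiDAC 123) and 19 days (HiDAC 135), SD 4 in both groups, 23 evaluable and 29 accrued per cohort (12.2). Last dose on Day 3 for HiDAC 123 and Day 5 for HiDAC 135 (3.1). Onset: "In general, the neutrophil nadir starts around Days 7-10 after HiDAC consolidation" (1.3). Duration is counted from the first ANC below 500 (2.1.2).

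**The plan's own figure.** A one-sided t-test at 0.05 with difference 3, SD 4 and 23 per group gives power of 80.5% (exact noncentral t) or 81.6% (normal approximation), against the stated 81%. Accrual is 23 / 0.80 = 28.75, rounded up to 29. Both reproduce, so the 16, 19 and SD 4 can be used as planned. The 28-day window has no stated figure of its own.

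**Closing day.** Last dose day + 28:
- HiDAC 123: 3 + 28 = Day 31.
- HiDAC 135, if the same clock were applied: 5 + 28 = Day 33.

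**Share still neutropenic at closing.** Assuming normal durations, P = 1 − Φ((closing day − onset day − mean) / SD).

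| Cohort, closing day | Onset | z | P | Expected of 29 |
|---|---|---|---|---|
| HiDAC 123, Day 31 | Day 7 | (31 − 7 − 16)/4 = 2.00 | 2.3% | 0.7 |
| HiDAC 123, Day 31 | Day 10 | (31 − 10 − 16)/4 = 1.25 | 10.6% | 3.1 |
| HiDAC 135, Day 33 | Day 7 | (33 − 7 − 19)/4 = 1.75 | 4.0% | 1.2 |
| HiDAC 135, Day 33 | Day 10 | (33 − 10 − 19)/4 = 1.00 | 15.9% | 4.6 |

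For HiDAC 123, the chance of at least one such subject among 29 is 1 − (1 − P)^29, which is 49% to 96%.

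**Alternative reading.** If the 16 days are time from the start of chemotherapy to recovery, z = (31 − 16)/4 = 3.75 and P is about 0.01%, or 0.003 of 29 subjects. For HiDAC 135, z = (33 − 19)/4 = 3.5 and P is about 0.02%.

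**Limits.** These are subjects still neutropenic, not missed events, which would be fewer. The clock restarts with each dose, so the exposure arises mainly after the last cycle, or when the next cycle is delayed beyond Day 31. The documents give no mean or SD for platelet recovery, so the transfusion share cannot be computed.

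**The case against.** The strongest reply is that much of the protocol already looks past 28 days. An infection needing admission is an SAE, and SAE collection has only a minimum length. Footnote 7 continues AE collection throughout the study. Section 11.1.1 has AEs assessed at each outpatient visit with no day limit, and transfusions are an endpoint per cycle with no end date. A subject with ANC below 500 on Day 31 already has an open hematologic toxicity, which 11.2 follows to resolution if related and 11.3 follows whether related or not. All of this stands, and it rules out saying that late events are lost or that SAE collection closes. It does not settle the matter. The follow-up rules concern events already open, and no text expressly requires a new non-serious event or transfusion after Day 31 to be recorded against the limits in 11.2 and footnote 6.

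Four stronger readings are tempting but not supported.

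- A reader might infer that HiDAC 123 will look safer than it is. That rests on silence: no window is stated for chart-abstracted controls, and nothing says they are abstracted for longer.
- A reader might infer that subjects who stop for toxicity lose their later counts and readmissions. The sentence in 8.2 reads that way alone, but later text in 8.2 and in 6.3 contradicts it.
- A reader might infer that the primary endpoint is truncated. Visits and labs run to recovery under 6.3.
- A reader might take a larger share by assuming that HiDAC 123 gives no shortening (19 days): 10.6% to 30.9%, or 3.1 to 8.9 of 29. The upper end implies mean recovery on Day 10 + 19 = Day 29, whereas 1.3 has most patients starting to recover on Days 21 to 24. Section 1.3 also cites times to recovery of 14-16 and 17-19 days from a retrospective study, close to the planned 16 and 19, which lends weight to the reading from Day 1.

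**Conclusion.** The concern holds as a conflict over when collection ends. Section 11.2 (AEs) and footnote 6 (transfusions) stop at Day 31 for HiDAC 123; 3.1, 6.3 and footnote 7 continue to recovery or throughout the study; 8.2 contains both a shorter and a longer rule. The result is unclear capture of new non-serious AEs, infections and transfusions in the slowest recoverers, mainly after the last cycle.

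The number affected ranges from almost none to about 3 of 29, depending on whether the planned 16 days start at onset (the definition in 2.1.2) or at Day 1. The estimate assumes normal durations and treats Day 7 to 10 as the first ANC below 500.

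The direction of any bias is not established. A last-dose clock applied to both cohorts would itself be unequal, since it gives HiDAC 135 two more days from Day 1. Secondary comparisons are exploratory (12.4) and safety is descriptive (12.6), so this affects the completeness and comparability of the safety data, not the primary test.

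**What to change.** Reconcile 3.1, 6.1 (footnotes 6 and 7), 6.3, 8.2 and 11.2 to one end of data collection for AEs, SAEs, infections, transfusions, readmissions and counts. That end is the later of 28 days after the last dose and documented neutrophil and platelet recovery from the last cycle, or earlier at a new regimen, HCT conditioning or death. Keep the existing follow-up of ongoing related events. Reconcile the end-of-treatment-date sentence in 8.2 with the follow-up-to-recovery text in 8.2 and 6.3.

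State the same window for the historical controls, counted from Day 1 of the cycle, so that the fixed part ends on the same day number in both cohorts.

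The cost is an amendment to the wording, a few more days of CRF entry for slow recoverers, and slightly higher event counts. The visits already take place under 6.3. The change concerns data collection only and leaves treatment as it is.
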